4.4 Results Disclosure

We expect results to be available within ~3-14 days of sample acquisition. We will monitor the patients' laboratory data to see when results have been finalized. Lab results and variant interpretations for the HOPE Genomics intervention will be stored in a custom genomic database designed by COH Research Informatics. All results will be validated by study staff before data are input into the HOPE-Genomics tool. All clinicians will receive results through the EHR. Additionally, clinicians with patients in the intervention arm will also be able to view their patients' results through the HOPE-Genomics after individual-level patient data have been entered into HOPE-Genomics. Results will be available to patients in the HOPE-Genomics app approximately 3-14 days after they are available in the EHR.

At this time, we will ask patients in the Return of Results Only intervention arm, (Arm 2) and the Return of Results + Pre-Test Education arm (Arm 3) to log into the HOPE-Genomics tool on their own time. Study staff will provide patients with instructions to create an account and log into the tool using dual-factor authentication. Study staff will track patients' tool access through Google Analytics and call or send automated RedCap reminders to encourage tool use, if necessary. Study staff will track patients' tool access through Google Analytics and call and/or send automated REDCap reminders to encourage tool use, if necessary. In addition, the study staff will be available to help patients access HOPE-Genomics at subsequent clinic/infusion visits or via secure web conference at any point in time following the disclosure of their test results until the end of the study (with coordination with the study team).

Patients in the control arm (Arm 1) will have their results returned in clinic by their provider, with no changes to the clinician's typical delivery method. Patients will be provided an educational pamphlet that generally describes sequencing and will granted access to the HOPE-Genomics tool with their results after completing all follow-up study surveys, approximately 9 months after their results are in the EHR.

As a thank you for their participation, patients will be provided with electronic or physical gift cards totaling \$25 throughout study participation. Patients will receive a \$5 gift card after completing the 10-day follow-up survey, a \$10 gift card after completing the 3-month follow-up survey, and a \$10 gift card after completing the 9-month survey. If patients require a separate study-specific visit to view HOPE-Genomics, we will provide them with a valet parking voucher to facilitate in-person study activities.

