3.3. Recruitment

We will enroll approximately 465 patients from City of Hope Duarte main campus and community locations. Patients will be identified in collaboration with the COH Precision Medicine (PM) team. [name], the study PI, is the Deputy Director of the Center for Precision Medicine and works closely with the entire PM team. Patients who have consented to COH IRB 07047, who are having genomic sequencing through 07047, and who have solid tumor diagnoses (see eligibility criteria below) will be eligible to participate. Patients will provide consent to this protocol at the start of their participation in the study and will subsequently be randomized into either the control arm (i.e., Usual Care), the Return of Results arm or the Return of Results plus Pretest Education arm.

In Clinic Recruitment

Potentially eligible patients will be approached by study team members during clinic visits for verbal informed consent. Patients will either be enrolled on site or given a study packet containing an invitation letter, informed consent document, return envelope, and a postcard to denote interest in participating or declination. Patients who do not return the postcard within 2-3 weeks will be contacted by a study team member to reassess interest in participating. Patients will be contacted either by telephone or web-conference or will be contacted at their next COH appointment in person. For patients interested in participating, study staff will schedule a verbal informed consent session by telephone, web-conference, or a patient's next COH appointment in person.

Remote Recruitment

When in-clinic recruitment is not feasible, potentially eligible patients will be contacted by study team members via telephone/email to gauge interest and potentially schedule a verbal consent session. If the patient cannot be reached, participants will be mailed a study information packet containing an invitation letter, informed consent document, return envelope, a postcard to denote interest in participating or declination. Study staff will also email patients to encourage contact. Patients who do not return the postcard within approximately 7-10 days weeks will be contacted by a study team member to reassess interest in participating, either by telephone or web-conference. Study staff will schedule a verbal informed consent session with patients who are interested in participating, either by phone or web-conference.

Waiver of Documentation of Informed Consent

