3.4. Cohort Characteristics and Eligibility

3.4.1 Patient Participants

Patients will be eligible if: 1) they are enrolled in COH IRB 07047, 2) have a cancer diagnosis, 3) they are having somatic, germline or paired somatic/germline sequencing, 4) they are fluent in English, 5) they have an ECOG performance status of 0-2, and 6) they are ≥ 18 years old.

Patients will be ineligible if they 1) are unable to provide informed consent.

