4.1.1 Patient Baseline Survey

At time of consent, patients will complete the baseline survey. Baseline survey outcomes are detailed in Table 1. We will follow standard survey methods as outlined by Dillman^{2,3} (e.g., contact type and intervals; mail/email/in-person reminders) to ensure high response rates. The survey will be administered in one of the following ways, according to patient preference: (1) mailed to the participant, along with a return envelope, (2) provided electronically and/or by text message via REDCap survey link, or (3) completed over a scheduled phone or Zoom call with a study staff member. For patients who complete the baseline survey via phone or Zoom call, study staff will not assist them in selecting the correct answers for questions pertaining to their understanding of cancer and genetics.

Germline sequencing knowledge will be measured using an adapted version of the UNC Genomics Testing Knowledge Scale¹, a validated 25-item measure developed by Langer and colleagues to evaluate overall understanding of genomics and health. We will also assess patients' knowledge of the implications of WES on 1) personal cancer risk, 2) family cancer risk, and 3) genetics generally.

General cancer genomics knowledge will be assessed using a modified form of a 12-item measure developed by Blanchette and colleagues.⁵ The measure assesses three domains of cancer genomic knowledge: 1) general understanding of cancer, 2) how biological changes influence cancer, and 3) the potential implications of genomic testing in cancer. Higher general cancer genomic knowledge has been associated with higher levels of education, higher personal income and patients' perceived ability to provide informed consent for genomic testing.

Knowledge about the use of genetic testing in cancer will be assessed using a 6-item measure developed by Roth, Gray and colleagues for the Lung-MAP study (unpublished). The measure assesses participant's knowledge of why genetic testing is used in cancer care (e.g., to help select a treatment, to predict response to treatment). Eight items have been added in the following content areas: 1) use for cancer staging, 2) use to time cancer onset, 3) use to predict treatment efficacy, 4) use for clinical trials, 5) use to monitor cancer treatment, 6) use to identify a cancer's location, 7) use to determine metastasis, and 8) use to assess cancer risk.

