4.3 Tool Access and Patient Pre-Education Survey

After enrollment, all participants will be provided with a hard-copy or electronic educational pamphlet about whole-exome sequencing (WES). Patients in the Return of Results plus Pre-test Education arm will be provided with login and dual-factor authentication instructions and have immediate access to educational content in the tool, with their sequencing results to become available in the tool shortly after their results are available in Epic. Patients in the Return of Results Only arm will not be able to see tool content until their genomic test results are available (e.g., ~2-6 weeks after sample collection). Patients in the Usual Care arm will have access to the tool content after completing all study surveys, approximately ~9 months after their sequencing results are available.

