Approximately 2-3 days after completing the baseline survey, patients in all study arms will complete a pre-test education survey that assesses general genomic knowledge prior to results disclosure. For patients requesting paper versions of the baseline and pre-test surveys, we will mail the pre-test survey 1 week after mailing the baseline. This will ensure that patients who opt for paper surveys can complete the pre-test survey within 2-3 days of completing their baseline survey. As with all study surveys, patients will also have the option of completing the pre-test education survey over a scheduled phone or Zoom call with a study staff member. During the phone or Zoom call, study staff will not assist patients in selecting the correct answers for questions pertaining to their understanding of cancer and genetics. As mentioned above, patients in the Return of Results plus Pre-test Education arm (Arm 3) will view the HOPE-Genomics tool prior to their results disclosure and completion of this survey. The HOPE-Genomics tool will be populated with educational material about genomics, cancer, and other related content, but without the patient's individual test results. We will track Arm 3 patients' tool access through Google Analytics, which is an IT-approved software that monitors user interaction metrics within the HOPE-Genomics platform, specifically button clicks per page, page scrolls, double clicks, and page-viewing duration times. We are utilizing Google Analytics to better understand which features of the tool are most frequently used by patients and identify technical aspects of the tool that need improvement. The version of Google Analytic implemented (GA4) in the HOPE-Genomics platform has a process of data anonymization, so no IP address or other PHI is collected from the participants. In addition, Google Analytics does not gather text data from the HOPE-Genomics platform and therefore has no access to potential PHI within the HOPE-Genomics platform. Additional security features of the HOPE-Genomics platform are discussed in Section 4.2 of this protocol (HOPE-Genomics Tool Details & Security Features). Study staff will call and/or email patients in the Return of Results plus Pre-Test Education arm within approximately 24 hours of receiving their login information to track whether patients interact with the HOPE-Genomics platform and if patients have not accessed the tool, study staff will encourage and facilitate intervention use. All other patients (Usual Care & Return of Results Only) will only view the WES pamphlet before completing this survey. The HOPE-Genomics educational content will be available to those patients in the Return of Results Only and Usual Care arms but will only be made available after their genomic test results are available in the tool.

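### Eligibility does not require the sequencing result to be unreleased at consent, so baseline, Arm 3 education and the pre-test survey can fall after release, chiefly for in-clinic patients who do not return the postcard

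*Combined protocol and SAP*

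**What the plan says.** **Who may enrol.** Section 3.4.1 requires that "they are having somatic, germline or paired somatic/germline sequencing". Section 3.3 describes the source patients as those "who are having genomic sequencing through 07047", and the physician letter (Appendix A) uses similar wording. All of this suggests testing in progress. None of it says that the result must still be outstanding at consent, or ties the sample date to approach or consent.

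**The intended order.** Section 4.1.1 states: "At time of consent, patients will complete the baseline survey". Under section 4.3 the pre-test survey follows 2-3 days later and is meant to precede disclosure, and Arm 3 is to view the tool before both. For paper users, "we will mail the pre-test survey 1 week after mailing the baseline".

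**Turnaround.** Section 4.4: "We expect results to be available within ~3-14 days of sample acquisition". Section 4.3 has Arm 2 waiting "until their genomic test results are available (e.g., ~2-6 weeks after sample collection").

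**Recruitment waits.** Section 3.3, in clinic: "Patients who do not return the postcard within 2-3 weeks will be contacted by a study team member to reassess interest in participating". Section 3.3, remote, with a garbled unit: "Patients who do not return the postcard within approximately 7-10 days weeks will be contacted".

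**The concern.** The design needs a window between consent and result release. Baseline, Arm 3's education and the pre-test survey all have to fit inside it. The protocol states the order but has no check that the window is open at enrolment and no rule for a result that arrives first. Staff watch the laboratory data under section 4.4, but that step has no stated role in eligibility or survey timing.

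The in-clinic re-contact wait of 2-3 weeks is as long as, or longer than, the whole 3-14 day turnaround in section 4.4. A patient recruited by that route can satisfy every criterion with the result already in the EHR.

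Two things are then at stake. The baseline recall item may be answered after the result is out. And the section 6.2.3 comparison of Arm 3 with Arms 1/2 on pre/post general knowledge, the analysis aimed at pre-test education, may include surveys that are not pre-result.

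**Working it through.** The documents give no figure for how many patients are out of order. The plan's only power figure (130 + 260 = 390, 80% power for 39% versus 54%) reproduces at 80.2%, but this point does not rest on it. The check is a day count.

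**Inputs**
- Result release: sample day + 3 to 14 (4.4), or + 14 to 42 (4.3).
- In-clinic re-contact of non-responders: day 14-21 (3.3). Remote re-contact: day 7-10 (3.3, reading the unit as days).
- Baseline: day of consent (4.1.1).
- Pre-test survey: baseline + 2-3 days, or mailed at + 7 days on paper (4.3).
- 10-day survey (T1): EHR release + 10 days (4.5.1).
- Sample day: not stated, so varied over 0, 7 and 14 days after approach.

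**Assumptions.** Day 0 is first approach. Consent happens on the re-contact day. Result availability means EHR release. Days are uniform within each stated range.

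**Formula.** If the survey day is uniform on a range lying inside the release range [a, b], the share of surveys after release is (mean survey day − a)/(b − a). If the survey range starts at or after b the share is 100%; if it ends at or before a the share is 0%.

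**In-clinic non-responders, sample on day 0**

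| Step | Days | 3-14 day results | 2-6 week results |
|---|---|---|---|
| Baseline | 14-21 | 100% | (17.5 − 14)/28 = 12.5% |
| Pre-test, electronic | 16-24 | 100% | (20 − 14)/28 = 21% |
| Pre-test, paper | 21-28 | 100% | (24.5 − 14)/28 = 37.5% |

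**Other routes, sample on day 0, 3-14 day results**
- On-site consent, prompt electronic pre-test, day 2-3: 0%.
- On-site consent, paper pre-test mailed day 7: (7 − 3)/11 = 36%. Completion comes after mailing, so the share at completion would be higher.
- Remote non-responders, baseline day 7-10: (8.5 − 3)/11 = 50%. Electronic pre-test day 9-13: (11 − 3)/11 = 73%.

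With 2-6 week results these four figures are all 0%.

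**Sensitivity to the sample date (in-clinic non-responders, pre-test survey)**
- Sample on day 7: 86% electronic and 100% paper with 3-14 day results; 2% and 12.5% (3.5/28) with 2-6 week results.
- Sample on day 14, 3-14 day results: release is day 17-28. Electronic: (7²/2)/(8 × 11) = 24.5/88 = 28%. Paper: (24.5 − 17)/11 = 68%.
- Sample on day 14, 2-6 week results: release is day 28-56, so 0% for both.

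**T1.** With the sample on day 0 and 3-14 day results, T1 falls due on day 3 + 10 = 13 to day 14 + 10 = 24. In-clinic non-responders consent on day 14-21, so T1 can be due around, or before, their consent.

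**What drives it.** The survey intervals alone (2-3 days, or 7 on paper) exceed neither turnaround range as a whole. The recruitment wait does.

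**The case against.** The strongest reply is that the intended sequence is stated several times. Section 6.1 describes baseline testing, then genetic testing and disclosure, then post-testing. The pre-test letter (Appendix J) treats testing as still to come, and the Arm 3 script (Appendix G) invites viewing before results are ready. If samples are drawn after baseline, the overlap shrinks or disappears. This stands as a limit on the claim: a reader might infer that the trial will enrol patients whose results are out, but without a sample date the documents show only that it can.

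Three further limits also stand.
- The 2-3 week wait applies only to in-clinic patients who have not returned the postcard. Card returners and on-site enrolees can consent sooner. The share of non-responders is not given, so the 100% figure must not be read as applying to every packet patient.
- EHR release is not disclosure. Sections 4.1.1 and 4.1.2 time recall from disclosure with a clinician, which may be later. Release is still the date that starts the T1 clock in section 4.5.1, and one that staff can check.
- A reader might infer that Arm 3 turns into Arm 2. It does not. Arm 3 has the educational content at once, while the other arms see only the pamphlet before the pre-test survey, and results reach the tool a further 3-14 days after the EHR. Lateness that arises before randomisation should also fall similarly on all arms.

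None of this supplies the missing criterion or a rule for results that arrive first.

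**Conclusion.** The point holds as a gap in eligibility and timing that should be closed. The rules as written allow baseline, Arm 3 education and the pre-test survey to fall after release, most plausibly for in-clinic non-responders under the 3-14 day turnaround. The size ranges from essentially all of that subgroup (sample by the day of approach, 3-14 day results) to none (sample 14 days later, 2-6 week results). It rests on an unstated sample date, uniform turnaround and consent on the day of re-contact. Prompt electronic surveys after on-site consent are unaffected throughout.

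The harm is mainly to baseline recall and to the exploratory knowledge comparison in section 6.2.3. It is tempting to conclude that the primary result is compromised, but the documents do not support that. Section 6.2.1 compares 10-day recall between randomised groups and names no adjustment for baseline recall. The remaining exposure is that T1 may fall due around consent for late responders.

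**What to change.** 1. Add to section 3.4.1: *no result of the index sequencing test has been released in the EHR at randomisation*. Staff check this on the day of consent, before the immediate randomisation described in section 4.1.
2. Record the dates of sample, EHR release, clinician disclosure, tool viewing and each survey.
3. Keep all randomised patients in the section 6.2.3 knowledge analysis. Add a prespecified sensitivity analysis that flags pre-test surveys completed after EHR release or disclosure.
4. Reconcile 3-14 days (4.4) with 2-6 weeks (4.3).

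Scheduling the pre-test survey to be due before release is not workable, because the release date is not known in advance.

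The cost is one eligibility line, one EHR check per patient and a few date fields. Because the check precedes randomisation, it introduces no post-randomisation selection. Some slow responders become ineligible. Section 3.1 expects about 4000 patients in year 1 and 6000 in year 2 against 465 places, but those are totals for protocol 07047 overall, not eligible patients with results pending. That the pool absorbs the loss is likely but not shown.

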4.5 Follow up Surveys

4.5.1 10-Day Follow-Up Survey

All patients enrolled in the study will be asked to complete a follow-up survey approximately 10 days after results are released in the EHR. The survey will either be mailed to the participant, provided electronically and/or by text message via REDCap survey link or completed over a scheduled phone or Zoom call with a staff member, according to patient preference. If the survey is mailed, the patient will be provided with a return envelope. Follow-up survey reminders will be similar to those outlined for the baseline survey. The follow-up survey outcomes are detailed in Table 1. For participants of both intervention arms, the survey will also include questions about the usability of HOPE-Genomics. Survey measures will be similar to measures detailed in Section 4.1.1.

Patients in Arm 1 (usual care) will receive a modified survey that does not contain questions that pertain specifically to the HOPE-Genomics tool, like usability.

4.5.2 3 Month Follow-Up Survey

Delivery of the follow-up survey and study materials will follow similar procedures mentioned in Section 4.3.1. The 3 Month follow-up survey outcomes are detailed in Table 1. Survey measures will be similar to measures detailed in Section 4.1.1.

4.5.3 9 Month Follow-Up Survey

Delivery of the follow-up survey and study materials will follow similar procedures mentioned in Section 4.4.1. The 9 Month follow-up survey outcomes are detailed in Table 1. Survey measures will be similar to measures detailed in Section 4.1.1. Participants in the Usual Care Arm will view their results in the HOPE-Genomics tool after completing the 39Month Follow-Up Survey. None of their follow-up surveys will contain questions pertaining to the HOPE-Genomics tool or its usability.

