11.0 APPENDICES

Appendix A: Physician Patient-Specific Recruitment Letter

Helping Oncology Patients Explore- Genomics (HOPE- Genomics) Web Tool Randomized Clinical Trial

[DATE]

Dear Dr. [PHYSICIAN LAST NAME],

We are writing to you because your patient, [PATIENT NAME, MRN], is eligible for participation in the HOPE-Genomics research study involving a web-based, patient-facing genomic education tool.

Please let us know if this is incorrect, or if you do not feel that this patient would be a good fit for our research study. We plan to otherwise approach your patient at a future clinic appointment or via email/mail/phone if we do not hear back from you over the next 24 hours. Please refer to the bottom of this email for the eligibility criteria of this study.

IF YOU DO NOT WISH FOR US TO CONTACT THIS PATIENT, PLEASE LET US KNOW. We will otherwise proceed with approaching him/her.

Note: If your patient enrolls in the study, your patient will have access to the HOPE-Genomics tool with HIS/HER genomic test results approximately 3 days after the results become available in EPIC.

For more information or questions about the study please contact the study Principal Investigator, [name], AM, or the Clinical Research Coordinator, [name] at [contact].

We look forward to hearing from you!

Thanks so much,

The HOPE-Genomics Team

[name], [name], [name], [name], and [name]

Division of Clinical Cancer Genomics

Medical Oncology and Therapeutics Research

Department of Population Sciences

City of Hope Comprehensive Cancer Center
[name]
[name]

[INSERT PATIENT NAME] is eligible because [HE/SHE]:

- Is receiving somatic, germline or paired somatic/germline sequencing through COH IRB 07047
- Has a cancer diagnosis
- Has an ECOG performance status of 0-2, and
- Is fluent in English

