Appendix H: Patient Script to Invite Viewing of Tool w/ Results – Either Intervention Arm

Dear [PATIENT NAME],

This is the HOPE-Genomics Team at City of Hope. You may remember speaking with [consenter] about your participation in the HOPE-Genomics study, involving a web-based education tool for patients with genetic testing at City of Hope. Thank you for completing your first two surveys for the study!

At this time, we would like to invite you to log into the tool to view your genetic test results. You may log into the tool by clicking the following link: <https://hopegenomics.coh.org/login>.

Once you have viewed the tool, we will send you a follow-up survey. We have also attached instructions for viewing the tool.

If you have any problems accessing the tool, we can accommodate in-person visits at City of Hope Duarte campus or remote visits using web conferencing (i.e. Zoom). Please call [INSERT CRA'S PHONE NUMBER] or email us at [contact] if you would like to schedule an appointment to speak with study staff.

If you have any additional questions about this research study, please call the Principal Investigator, [name] at [contact] or the Clinical Research Coordinator, [name] at [contact]. You can also reach the Institutional Review Board at City of Hope by calling [contact].

Thank you for all your help with our research at City of Hope, and we look forward to hearing from you!

The HOPE-Genomics Team

[name], [name], [name], [name], and [name]

Division of Clinical Cancer Genomics

Medical Oncology and Therapeutics Research

Department of Population Sciences

City of Hope Comprehensive Cancer Center

[name]

[name]

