Appendix K: Follow-Up Survey Invitation Letter (10 day/3 month/9 month for Intervention Arms)

Dear [PATIENT NAME],

This is the HOPE-Genomics team at City of Hope. You may remember speaking with [consenter] recently about your participation in the HOPE-Genomics study. Thank you for viewing your genomic test results in the HOPE-Genomics tool for patients at City of Hope!

To help us make this tool the best it can be, we would love to hear your thoughts. There will be 3 follow-up surveys, approximately 10 days, 3 months, & 9 months after receiving your genomic test results. This is the [SURVEY NAME]. This survey will ask you about cancer, genetics, and what you understand about your genetic testing results and cancer. The survey may also ask you about your experience viewing your test results in the HOPE-Genomics tool. Some of the questions may look familiar from an earlier survey. We would like you to complete this survey as well.

[For REDCap]. You can access the [SURVEY NAME] online by using this link: [LINK]. Please complete the survey, using the provided study ID: [INSERT STUDY ID].

[PAPER ONLY]. Please complete the attached survey and mail it back to us in the enclosed self-addressed return envelope.

After completing this survey, you will be provided with a [INSERT 5/\$10] gift card as a thank you for your time and feedback.

Participation in this study will not involve any treatment. The study is confidential and your responses to survey questions will not be passed along to your medical provider or anyone outside of the study team.

If you have any questions about this research study, please call [CONSENTER'S NAME] at [INSERT CONSENTER'S PHONE NUMBER], or the Principal Investigator, [name] at [contact] or the Clinical Research Coordinator, [name] at [contact]. You can also reach the Institutional Review Board at City of Hope by calling [contact].

Thank you so much,

The HOPE-Genomics Team

[name], [name], [name], [name], and [name]

Division of Clinical Cancer Genomics

Medical Oncology and Therapeutics Research

Department of Population Sciences

City of Hope Comprehensive Cancer Center

[name]

[name]

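### The primary 10-day recall survey has conflicting start dates, can fall due before results are in the tool, and is tied to tool viewing or access in intervention-arm materials

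*Combined protocol and SAP*

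**What the plan says.** **When T1 is due.** Section 4.5.1: "All patients enrolled in the study will be asked to complete a follow-up survey approximately 10 days after results are released in the EHR". Sections 4.1.1 and 4.1.2 place the recall assessment 10 days after a clinician discloses the results. The Table 1 footnote and Section 6.2.1, which defines the primary analysis, say only that it follows disclosure. The Arm 2/3 letter (Appendix K) counts "approximately 10 days, 3 months, & 9 months after receiving your genomic test results". The Arm 1 letter (Appendix L) gives about two weeks from receipt, although it also calls the survey the 10-day one.

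**When results reach the patient.** Section 4.4: "Results will be available to patients in the HOPE-Genomics app approximately 3-14 days after they are available in the EHR". Appendix A tells physicians "approximately 3 days after the results become available in EPIC", and Section 4.3 also describes a short delay after Epic for Arm 3. For usual care, Section 4.4 says "Patients in the control arm (Arm 1) will have their results returned in clinic by their provider" and gives no time.

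**Viewing and access.** Appendix H, used for both intervention arms: "Once you have viewed the tool, we will send you a follow-up survey". Appendix K opens "Thank you for viewing your genomic test results in the HOPE-Genomics tool". In Appendix M, a patient who has not viewed the tool and declines an appointment for help is told that participation cannot continue without access and that their data will be removed. Section 8.7 instead lets the participant choose among four forms of withdrawal.

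**Analysis.** Section 6.2.1 pools Arms 2 and 3 (n = 260) against Arm 1 (n = 130) and describes the pooled group as having had some exposure to the tool. Intention-to-treat is named only for Aim 2, in Section 6.2.2.

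**The concern.** Recall at T1 is the primary endpoint and the only one with a power statement. For a recall measure, the time since the patient learned the result is part of what is measured, so time zero has to be the same event in every arm. EHR release, clinician disclosure, receipt of results and tool viewing are four different events, and the documents use all four.

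Two distinct harms follow. If Section 4.5.1 is applied with the Section 4.4 lag, some intervention patients answer before the tool has given them their results, which dilutes the comparison. If the wording of Appendices H and M is applied, patients who do not view or cannot access the tool drop out of Arms 2/3 only, because of behaviour after randomisation. The comparison is then no longer between randomised groups, and the bias can go either way.

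**Working it through.** **1. The plan's own figure.** Inputs from Section 6.2.1: 39% in Arm 1 (n = 130), a 15-point gain to 54% in Arms 2/3 (n = 260), two-sided alpha 0.05.

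Power = Φ[(d − 1.96·SE₀)/SE₁], where SE₀ uses the pooled proportion and SE₁ the two separate proportions.

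- Pooled proportion = (130×0.39 + 260×0.54)/390 = 0.49
- SE₀ = √[0.49×0.51×(1/130 + 1/260)] = 0.0537
- SE₁ = √[0.39×0.61/130 + 0.54×0.46/260] = 0.0528
- Power = Φ[(0.15 − 0.1052)/0.0528] = 80.2%

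The stated 80% reproduces.

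**2. Do the intervals overlap?** The survey is due at day 10 after EHR release and tool release falls on days 3–14. A patient with a 3-day lag has results in the tool for 7 days before T1 is due. A patient with a 14-day lag gets them 4 days after. Section 4.4 leaves viewing to the patient's own time, and Section 4.3 sets the text reminder 5 days after login instructions. If those instructions go out at tool release, the reminder comes after day 10 for any lag above 5 days.

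**3. Dilution under Section 4.5.1.** Assumptions not in the documents: 15 points is the effect once results are in the tool; patients without them recall at the usual-care 39%; the lag is uniform on 3–14 days; answers spread evenly over S days after day 10. The share surveyed before release, for S ≥ 4, is

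u = (1/S)·∫₀⁴ (4 − a)/11 da = 8/(11·S), and the difference is 15×(1 − u).

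| Case | u | Difference (points) | Power, 130 vs 260 |
|---|---|---|---|
| All lags about 3 days | 0 | 15.0 | 80.2% |
| S = 21 days | 3.5% | 14.5 | 77.3% |
| S = 14 days | 5.2% | 14.2 | 75.8% |
| S = 7 days | 10.4% | 13.4 | 71.0% |
| S = 4 days | 18.2% | 12.3 | 63.1% |
| All on day 10, whole-day lags (4 of 12 days) | 33.3% | 10.0 | 46.3% |
| All on day 10, continuous lag (4/11) | 36.4% | 9.5 | 43.0% |

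**4. Gate under Appendices H and M, no true effect.** Let v be the share of non-viewers and r their recall, both assumed. Remaining recall in Arms 2/3 is (39 − v·r)/(1 − v), with n = 260(1 − v), against 39% in 130.

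| v | r | Recall left in Arms 2/3 | False difference (points) | Two-sided error rate |
|---|---|---|---|---|
| 10% | 29% | 40.1% | +1.1 | 5.5% |
| 10% | 49% | 37.9% | −1.1 | 5.5% |
| 20% | 29% | 41.5% | +2.5 | 7.3% |
| 20% | 49% | 36.5% | −2.5 | 7.5% |
| 10% or 20% | 39% | 39.0% | 0 | 5.0% |

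**The case against.** The best defence is that Section 4.5.1 governs, surveys all enrolled patients on one clock and sets no viewing condition, while the conflicting wording sits in letters and scripts. Much of this stands. Appendix G uses the same once-viewed sentence for the pre-test survey, yet Section 4.3 times that survey from baseline: "Approximately 2-3 days after completing the baseline survey, patients in all study arms will complete a pre-test education survey". The Appendix H sentence may therefore be stock wording. Appendix K only thanks the patient and sets no condition. The two weeks in Appendix L may be a slip. Section 4.3 and Appendix A both point to a short release lag.

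A reader might infer from the exposure wording in Section 6.2.1 that only viewers will be analysed. The documents do not support that: n = 260 is two full analysed arms of 130, the arms are pooled as such, and Section 4.5.1 surveys everyone enrolled. Analysis by assigned arm is the natural reading.

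A reader might also infer that the difference will be inflated because some usual-care patients have not yet been told their results by day 10. No disclosure times are given, so this cannot be sized. The 39% pilot rate may already include such patients, and earlier direct access to results is part of the intervention described in Sections 1.0 and 2.0.

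The defence does not remove three things: Sections 4.1.1 and 4.1.2 are body text and contradict Section 4.5.1; day 10 lies inside the lag in Section 4.4; and the Appendix M instruction is specific and departs from Section 8.7.

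**Conclusion.** The point holds and should be fixed. Confidence is high that the passages conflict and low on how much it matters.

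The power cost runs from none, if lags are about 3 days, to a fall to 43% if lags are uniform and everyone answers on day 10. The low end should not be read as the expected power: the survey date is approximate, and Section 4.1.2 has a 2–3 week follow-up window for completion. Neither is 76–77% a safe central value, because that window says nothing about when answers actually arrive. Arm 3's earlier education could make the dilution smaller. Results released but not yet viewed could make it larger.

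The gate figures, up to 2.5 points either way and an error rate of 5.0–7.5%, apply only if the appendix wording is enforced, with 10–20% non-viewers whose recall is 29–49%. The documents do not show that it is enforced, and they do not announce a viewer-only analysis. They lack an explicit as-assigned statement for the primary endpoint.

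**What to change.** 1. Adopt one time zero and one T1 window for all three arms. The EHR release date of Section 4.5.1 exists in every arm. Bring the Table 1 footnote, Sections 4.1.1, 4.1.2 and 6.2.1, and Appendices K and L into line.
2. Send T1 by calendar whether or not the tool was viewed. Delete the viewing condition in Appendix H, adjust the opening of Appendix K, and replace the stop-and-remove statement in Appendix M with the options in Section 8.7. Align Appendix G with Section 4.3.
3. State in Section 6.2.1 that all randomised patients with T1 data are analysed in their assigned arm, including non-viewers and those surveyed before tool release.
4. Give the T1 usability items only to patients who have viewed the tool, as Section 4.1.2 intends.
5. Reconcile the tool-release times in Sections 4.3 and 4.4 and Appendix A with each other and with the day-10 survey. Which schedule is right is for the study team to settle.
6. Record the dates of EHR release, tool release, first viewing and survey completion, and of clinician disclosure where available. As a sensitivity analysis, report by arm how many answered before tool release or before disclosure.

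**Cost.** Wording amendments and some extra date abstraction (clinician disclosure is not among the items listed in Section 4.6), but no extra patients. Appendix U shows that patients had already consented, so any T1 data already collected need separate handling. With an EHR anchor some patients may still answer before their clinician has told them. The recorded dates show this but do not remove it.
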